9.6.1 Product Equipment

9.6.1.1 FlowMet-R

The FlowMet-R is a non-invasive optical device that measures real time blood flow/perfusion rate in the extremities using the principles of laser speckle imaging (LSI). To perform LSI, tissue is illuminated with coherent laser light, which scatters off moving red blood cells and produces a speckle pattern. The pattern is recorded on an image sensor and the characteristics can be used to measure blood flow/perfusion, as demonstrated in prior literature [26].

During use, the FlowMet-R probe is affixed onto the toes using a spring-loaded clip, with the light source (laser diode) and image sensor (digital camera) on opposite sides. The image sensor and readout circuitry are custom designed for a compact profile and adequate spatial sampling of the speckle pattern [27]. Molded, biocompatible silicone pads are used within the FlowMet-R probe in locations where the device contacts skin. Data acquisition, processing, display, and user interaction is performed using custom software run on a computer with Windows 10 operating system. Between uses, the skin-contacting silicone pads and probe housing can be sanitized using alcohol wipes or germicidal wipes, such as PSI Inc. Sani-Cloths, which are commonly used in hospitals and which are bactericidal, tuberculocidal, and virucidal. The FlowMet-R has been used in NSR-designated IRB approved studies on

more than 100 patients without adverse events. The FlowMet-R was 510(k) cleared by the FDA in early March, 2019.

If the FlowMet-R system malfunctions and/or needs to be serviced, this will be reported on the EDC and to Medtronic. Medtronic will provide technical assistance within 48 hours. If the system requires repair or replacement, Medtronic will provide a new unit to the site within 5 business days.

9.6.1.2 Automatic ABI System

Medtronic will provide an automated PAD system, the Flolab (Parks Medical Electronics, Inc., Aloha, OR) which will be provided to each site by Medtronic and used to perform ABI and TBI measurements. An automated device can improve measurement consistency between sites and help reduce inter-operator differences. The system includes a 4 Piece set of standard 8½"-14" (22 cm-36 cm) cuffs, a PPG monitor, and a control unit, which is used to automatically perform bilateral ABI and TBI measurements. Measurements results will be printed out and included in the CRF. If the automated system cannot be used or is unavailable, manual ABI and TBI measurements will be performed. Clinical personnel must be trained on use of the Flolab device prior to taking ABI and TBI measurements with the system.

9.7 Standard Noninvasive Vascular Assessments

Noninvasive testing and Duplex imaging results will be evaluated on the same leg(s) used to collect FlowMet-R data with the patients lying supine. The results will be recorded on the CRF. If color duplex imaging is not scheduled as standard of care, angiographic images taken within 30 days prior to the noninvasive measurements may be used for calculation of stenosis percentage.

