Secondary Objective(s) and/or Endpoint(s)	The secondary objectives are to determine the capability of the FlowMet-R in prognosis of requiring vascular intervention or amputation within three and six months following the initial visit. Additionally, to investigate the correlation between FlowMet-R measurements and peripheral artery stenosis. Finally, to assess the correlation between changes in ABI/TBI/Rutherford Classification and changes in FlowMet-R data between any two time points.
Study Design	Multi-center, non-randomized, longitudinal study with three and six month follow-up.
Sample Size	PAD Cohort: Cohort will consist of 240 limbs with PAD including a minimum of 54 limbs with claudication and a minimum of 100 limbs with CLI. All comers - any patient scheduled for peripheral vascular

	
assessment who is not subject to exclusion may be approached for enrollment in the disease positive arm. Exclusion criteria are detailed in Section 8.4. This will include patients in the registry who have a planned endovascular or surgical intervention to address their PAD.
 
Healthy Cohort: Cohort will consist of 160 control limbs. Any patient over 40 years old and without suspected PAD may be approached for enrollment in the healthy control arm. Healthy subjects may be enrolled from other departments within the clinic/hospital, can be from the local community, or can be actively recruited for participation (such as researchmatch.com or active volunteers).
 
Registry: Patients diagnosed with PAD at baseline procedure who are scheduled to undergo an endovascular treatment of the lower limbs will be included in the registry data for this study. The registry will be established to record FlowMet-R measurements, angiographic films, and any additional relevant information immediately prior to, during, and immediately following peripheral vascular interventional procedures for enrolled patients.

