4.1.2.1 Secondary Endpoints

- Utilize FlowMet-R data to create a predictive model for the prognosis of vascular intervention within a three and six month timeframe from initial visit.
- Employ the predictive model of PAD severity to generate an ROC curve for diagnosis of significant stenosis (>50%) in the iliac, femoral, popliteal, peroneal, or tibial arteries.
- Conduct a correlation test between the predictive model of PAD severity and greatest percent stenosis in the iliac, femoral, popliteal, peroneal, or tibial arteries.

- Conduct a correlation test between changes in the predictive model of PAD severity and corresponding changes in ABI, TBI, and Rutherford Classification between any two study time points.

5. Study Design

This is a non-randomized, multi-center, longitudinal study of healthy subjects and subjects with PAD who are scheduled for ABI, TBI, and either Duplex ultrasound or Angiographic assessments in a vascular clinic. As detailed in the Event Schedules (Section 9.1), subjects will first be evaluated for study inclusion/exclusion. If the subject meets the inclusion criteria and wishes to enroll in the study, they will be asked to sign an informed consent form (ICF) and considered for enrollment. If the subject meets inclusion criteria and is enrolled, the subject will undergo approximately 3 minutes of FlowMet-R blood flow measurements in addition to their routine standard of care examination.

Subjects enrolled in the PAD cohort will be assessed according to Event Schedule A at approximately 0, 3 months, and 6 months. Subject follow ups must meet the scheduled time window within +/- 30 days. Subjects that require a vascular (re)intervention for PAD-related treatment before the final measurement (6 month follow up) will have pertinent data collected and saved in the study registry. The vascular procedure may change the timing with respect to the amount of months after baseline that the follow up visits occur. In that case, the standard of care follow up visits post intervention will be adhered to, and data will be collected from the follow up visits that correspond most closely to timepoints at 3 and/or 6 months post baseline visit.

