8.4 Exclusion Criteria

Candidates for this study who meet any of the following criteria at the time of the baseline visit are NOT eligible to be enrolled in this study:

PAD Positive Cohort Exclusion

- Subject is under 40 or unable to consent.
- Subject has any medical condition, which, in the judgment of the Investigator and/or designee, makes the subject a poor candidate for the investigational study.
- Subject is excluded from analysis if no stenosis is found during Doppler but Tibial disease is suspected and Tibial ultrasound is not able to be performed.
- Subject does not have a suitable finger to attach the FlowMet-R probe.
- Subject does not have a suitable 1st or 2nd digit to attach FlowMet-R probe on the limb of interest.
- Subject has undergone revascularization within the last 90 days

- Subject cannot lay safely in a supine position.

Healthy Cohort Exclusion

- Subject is under 40 or unable to consent.
- Subject has any medical condition, which, in the judgment of the Investigator and/or designee, makes the subject a poor candidate for the investigational study.
- One or more limbs has a prior or current diagnosis of PAD, or is reasonably suspected of having a diagnosis of PAD.
- Subject does not have a suitable finger to attach the FlowMet-R probe.
- Subject does not have a suitable 1st or 2nd digit to attach FlowMet-R probe.
- Subject has undergone revascularization within the last 90 days

9. Study Procedures

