9.7.4 Duplex ultrasound

Color duplex ultrasound measurements shall be used to determine stenosis percentage and location, either during the visit itself or within 30 days prior of the patient visit. Duplex shall be acquired from all limbs enrolled in the study with PAD/CLI as defined via the definitions in Section 8.4. If duplex ultrasound is not available, X-ray angiography will be considered a suitable alternative for calculation of stenosis and location. Color duplex ultrasound imaging will be performed in a similar fashion as the study by Lewis, et al. [30]. First, the distal common femoral artery (CFA) will be imaged and the Doppler waveform (DW) assessed visually for any loss of triphasic flow due to significant iliac disease. If the DW shows indications of this, then the iliac arteries will be assessed for the presence of atherosclerotic disease. The scan will continue distally from the CFA assessing the superficial femoral artery (SFA), popliteal, anterior tibial, posterior tibial, and peroneal arteries in the longitudinal plane. The extent and severity of any arterial disease are assessed by measuring the peak systolic velocity (PSV) from the DW just proximal to and distal through the stenosis. For each measured artery, if perceptible stenosis exists, the location of maximum stenosis will be identified and PSV values distal and proximal to the arterial stenosis will be noted on the CRF. The shape of the waveform (i.e. monophasic, biphasic, or triphasic) measured distal to the stenosis shall also be noted. If no stenosis is noted, this will be indicated on the CRF.

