9.7.5 X-Ray Angiography

Peripheral angiography may be used as an alternative to duplex ultrasound in the assessment of arterial stenosis percentage and location, and may be performed during the visit itself or within 30 days prior. Angiography is an imaging technique to diagnose narrowed or blocked peripheral arteries, the hallmark of PAD. Angiograms may or may not include dye for improving image contrast. Angiograms have been used for decades and are considered the gold standard for evaluating vascular disease. Advanced techniques, such as the computed tomographic angiogram (CTA), and digital subtraction angiography (DSA) have gained popularity in recent years and have shown reliable sensitivity and specificity for differentiating extend of disease [31].

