7.1.3 Analysis Sets

Full Analysis Set

The full analysis set will include all participants and be used for all analyses. Visits outside of visit windows will be assigned to the nearest window. If a participant is missing data for a specific analysis, they will be excluded for that analysis. Within the analysis set, the grouping participants into the healthy, PAD (definitions 1 and 2), and CLI groups are defined in section 4.1.1.1.

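### The 30-day look-back for stenosis imaging does not require that the limb was untreated between the image and the FlowMet-R reading, which leaves any follow-up stenosis pairs unprotected

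*Protocol*

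**What the plan says.** **Look-back.** Duplex is the usual source of percent stenosis, obtained "either during the visit itself or within 30 days prior of the patient visit" (Protocol 9.7.4). Angiography is the fallback. Under 9.7, when duplex is not scheduled, "angiographic images taken within 30 days prior to the noninvasive measurements may be used for calculation of stenosis percentage"; 9.7.5 repeats that it "may be performed during the visit itself or within 30 days prior". None of the three sections mentions a procedure falling between image and reading. The version history justifies 30 days by the stability of stenosis in chronic PAD over that interval.

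**Revascularisation.** The only restriction is the exclusion "Subject has undergone revascularization within the last 90 days" (Protocol 8.4; repeated in SAP 5.6). It sits under a lead-in stating that candidates who meet a criterion "at the time of the baseline visit are NOT eligible to be enrolled in this study".

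**Treatment during the study.** On enrolment of the PAD cohort, the synopsis says: "This will include patients in the registry who have a planned endovascular or surgical intervention to address their PAD". Protocol Section 5 lets procedures occur at any point from the initial visit to the 6-month visit. For treated subjects, "the standard of care follow up visits post intervention will be adhered to", and the visits nearest months 3 and/or 6 supply the data.

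**Analysis.** SAP 7.1.3: "The full analysis set will include all participants and be used for all analyses". The only stated reason for leaving a participant out of an analysis is missing data. SAP 7.10.2 names no visit for the stenosis ROC (item 2) or the stenosis correlation (item 3).

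**The concern.** The look-back rests on stenosis being nearly constant over 30 days. Revascularisation is meant to change stenosis, so the justification does not cover a limb treated inside those 30 days. At baseline the 90-day exclusion rules that case out. After baseline no equivalent condition appears in the text, and the design expects interventions.

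If such a pair entered the stenosis analyses, the limb would carry its pre-treatment stenosis label beside a FlowMet-R value taken after treatment. Two secondary endpoints are at stake: the ROC for significant stenosis and the correlation with greatest percent stenosis. The label would be wrong for the moment of the reading, and the likely effect is to understate the association.

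**Working it through.** The plan gives no figure on this point, so there is none to reproduce. The check has three parts.

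**1. Which pairs are protected.** Inputs: look-back 30 days (Protocol 9.7, 9.7.4, 9.7.5); exclusion 90 days, applied at baseline (8.4); follow-up windows of months 2 to 4 and 5 to 7 (9.3). Months are taken as 30 days.

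- Baseline: the image is at most 30 days old and no procedure is allowed in the previous 90 days. Since 30 < 90, no procedure can lie between image and reading.
- Follow-up 1: the look-back covers days 60 to 90 for a visit on target, and days 30 to 120 across the whole window.
- Follow-up 2: days 150 to 180 on target, and days 120 to 210 across the window.

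All the follow-up intervals lie after day 0, where the exclusion no longer acts. Example: image and procedure on day 75, visit on day 95. The image is 95 − 75 = 20 days old, inside the look-back, and day 95 is inside the first window (days 60 to 120). No written imaging or visit-timing rule rejects the pair, provided the image is otherwise an accepted source; for an angiogram, that means duplex was not scheduled or not available.

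**2. How many procedures could be involved.** Assume procedure dates uniform over days 0 to 180 and both visits on target. The share falling within 30 days before a follow-up visit is (30 + 30)/180 = 33%. At the registry's minimum of 25 procedures, 25 × 0.33 is about 8. With 240 PAD limbs and two follow-up visits there are 240 × 2 = 480 scheduled follow-up limb-visits, so 8/480 = 1.7%, taking one limb per procedure, full attendance and a pre-treatment image used every time. The share among stenosis-positive limb-visits would be larger because the denominator is smaller. The total number of procedures could also exceed 25, which is a floor. The documents give neither figure.

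**3. Effect for an assumed share f.** For the ROC, f is the share of stenosis-positive limb-visits that are mismatched. Assume these read like non-stenosed limbs:

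AUC observed = (1 − f) × AUC + f × 0.5

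For the correlation, f is the share of all pairs. Assume mismatched pairs contribute no association and leave means and variances unchanged:

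r observed = (1 − f) × r

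| f | AUC 0.80 | AUC 0.67 | r 0.60 (assumed) |
|---|---|---|---|
| 5% | 0.785 | 0.661 | 0.57 |
| 10% | 0.770 | 0.653 | 0.54 |
| 20% | 0.740 | 0.636 | 0.48 |

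The AUCs of 0.80 (CLI) and 0.67 (claudication) are the pilot values in Protocol 12.1.1, borrowed for scale. They are not stenosis AUCs. If treated limbs stay partly abnormal, the AUC loss is smaller. For Pearson's r, clearly discordant points could cost more than the table shows.

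**The case against.** The strongest reply is that the text permits the mismatch without showing that it will occur.

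- No visible text requires stenosis to be paired with FlowMet-R data at month 3 or 6. Table 2 in Protocol 9.2 lists no stenosis imaging at follow-up. It lists none at baseline either, although 9.7.4 calls for duplex on enrolled PAD/CLI limbs, so it does not settle the question. Event Schedule A, which covers initial and follow-up visits, is a figure not available in the text reviewed and may settle it.
- SAP 7.10.2 item 3 lists visit intervals for the ABI and TBI changes but none for stenosis. That fits a single baseline stenosis value at least as well as repeated ones.
- Angiography may be used only when duplex is not scheduled or not available, so an angiogram from a procedure is not automatically the stenosis source.
- Procedural films are registry data, for which Protocol Section 5 sets no objective or endpoint. They may include frames taken after treatment.
- SAP 7.10.2 item 2 describes a stenosis ROC but names vascular intervention or amputation within 7 months as its outcome. Until that is corrected, the effect of a wrong stenosis label cannot be traced through that analysis as written.
- The analyses are secondary and descriptive, and the probable error runs against the device.

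All of this stands and limits the size and certainty of the point. It does not supply the missing condition. Duplex has the same gap as angiography, and neither document confines the stenosis analyses to baseline.

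**Conclusion.** The gap is real but conditional. Followed as written, the 30-day rule admits a pre-treatment image beside a post-treatment reading at follow-up, contrary to the rule's own rationale. It matters only if stenosis is analysed at month 3 or 6, which the SAP leaves open. If it is, the secondary stenosis ROC and correlation would probably move toward no association: by 0.017 to 0.030 in AUC at an assumed 10% of positive limb-visits (0.67 − 0.653 and 0.80 − 0.770), and by nothing if only baseline is used.

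A reader might infer three stronger things that the documents do not support:

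- **That the stenosis results will be biased.** Follow-up pairing is neither required nor excluded, and the affected share is not given.
- **That each procedure's own films will label treated limbs as stenosed.** Those films belong to the registry, may include post-treatment frames, and are at most a fallback source.
- **That the main diagnostic claim is weakened.** The PAD and CLI definitions use ABI, TBI, post-exercise ABI and symptoms, with no imaging, so the primary analyses are untouched.

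The change is worth making because it is cheap and settles beforehand which image counts.

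**What to change.** **SAP 7.10.2.** State that the baseline visit is the main stenosis analysis. State that a follow-up limb-visit is excluded from the stenosis ROC and correlation when its stenosis image predates a revascularisation of that limb, and that imaging after the treatment qualifies. In item 2, replace the outcome of vascular intervention or amputation with the stenosis outcome.

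**Protocol 9.7, 9.7.4 and 9.7.5.** Add the matching data-pairing condition: an image supplies percent stenosis for a visit only if that limb has not been revascularised between the image and the FlowMet-R reading.

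**Cost.** A few sentences in two documents and a check of image dates against logged procedure dates. Some follow-up limb-visits leave the stenosis analyses, which lowers precision there. No new imaging is needed and patient care does not change. If the sponsor intends stenosis to be analysed at baseline only, saying so in SAP 7.10.2 closes the pairing gap by itself; item 2 still needs its correction.

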9.7.1 Toe brachial index (TBI)

A patient rest period shall be performed in accordance with standard ABI/TBI collection before FlowMet-R or ABI/TBI measurement. Brachial pressures and toe pressures on both lower limbs (if applicable) will be measured according to the 2016 guidelines provided by the ACC/AHA using an automated TBI system. A PPG device will be used to detect the toe waveform. Measurement results will be recorded on the CRF.

9.7.2 Ankle brachial index (ABI)

A patient rest period shall be performed in accordance with standard ABI/TBI collection before FlowMet-R or ABI/TBI measurement. Brachial pressures and ankle pressures on both lower limbs (if applicable) will be measured according the 2016 guidelines provided by the ACC/AHA using an automated sphygmomanometer-based system. Measurement results will be recorded on the CRF.

9.7.3 Postexercise ankle brachial index (ABI)

If an enrolled patient's ABI and TBI measurements classify that patient as not having PAD/CLI as per the definitions in Section 8.4, but it is suspected that the patient may have PAD based upon medical history or clinical symptoms, a postexercise ABI measurement will be performed. For such patients, guidelines

provided by the ACC/AHA will be followed. A treadmill or heel-raise test will be considered an acceptable challenge for measurement of postexercise ABI.

9.7.4 Duplex ultrasound

Color duplex ultrasound measurements shall be used to determine stenosis percentage and location, either during the visit itself or within 30 days prior of the patient visit. Duplex shall be acquired from all limbs enrolled in the study with PAD/CLI as defined via the definitions in Section 8.4. If duplex ultrasound is not available, X-ray angiography will be considered a suitable alternative for calculation of stenosis and location. Color duplex ultrasound imaging will be performed in a similar fashion as the study by Lewis, et al. [30]. First, the distal common femoral artery (CFA) will be imaged and the Doppler waveform (DW) assessed visually for any loss of triphasic flow due to significant iliac disease. If the DW shows indications of this, then the iliac arteries will be assessed for the presence of atherosclerotic disease. The scan will continue distally from the CFA assessing the superficial femoral artery (SFA), popliteal, anterior tibial, posterior tibial, and peroneal arteries in the longitudinal plane. The extent and severity of any arterial disease are assessed by measuring the peak systolic velocity (PSV) from the DW just proximal to and distal through the stenosis. For each measured artery, if perceptible stenosis exists, the location of maximum stenosis will be identified and PSV values distal and proximal to the arterial stenosis will be noted on the CRF. The shape of the waveform (i.e. monophasic, biphasic, or triphasic) measured distal to the stenosis shall also be noted. If no stenosis is noted, this will be indicated on the CRF.

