The ankle brachial index (ABI) is perhaps the most widely used screening technique to diagnose PAD. While the ABI is relatively simple to perform, it is a ratio of systolic blood pressures rather than a direct measurement of blood flow, and, despite its widespread usage, is only a proxy of direct perfusion measurements. Generally, a cutoff of $ABI < 0.91$ is used to predict the presence of PAD, and a cutoff of $ABI < 0.4$ is used to predict the presence of severe PAD indicating CLI [14]. In diagnosing >50% stenosis of lower limb arteries, researchers have found the ABI to have relatively high specificity, ranging from approximately 83%-99%, but highly variable sensitivity, ranging approximately 15%-79% [15]. In patients with partially non-compressible arteries, ABI values may be inflated and appear normal, despite the presence of significant disease. When the ABI is in a normal range but PAD is suspected, a postexercise ABI may be used to provide additional confirmation. A drop in >30mmHg ankle pressure or

ABI of >20% after exercise indicates the presence of significant disease [16]. The postexercise ABI may be performed with a treadmill test or repeated heel-raises [16].

While ABI has a relatively good sensitivity and specificity for claudication, recent data has shown that over 30% of patients with documented CLI have a normal ABI or ABI consistent with non-compressible blood vessels [17-19]. Therefore, in patients with wounds and/or gangrene, TBI is often used to assist in confirmation [20].

Color duplex ultrasound (CDU/CDI) imaging is often considered the gold standard when assessing arterial stenosis in a vascular laboratory, and good agreement has been shown between duplex and digital subtraction angiography (DSA) [21]. Generally, when assessing the performance of other diagnostic metrics such as ABI, Duplex ultrasound may be used as a gold standard to determine presence of >50% stenosis, indicating significant PAD [15, 22].

While the noninvasive technologies mentioned above are considered standard of care in vascular medicine, there remains a lack of simple and continuous methods to assess PAD severity. A portable technology capable of quantifying disease severity simply and in real time could significantly ameliorate diagnosis, surgical treatment, and follow up care.

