4.1.1.1.1 Definitions of PAD and CLI

- Two types of positive diagnosis of PAD will be explored according to published literature: (1) $ABI \leq 0.9$ or $ABI > 1.4$ and secondary verification of $TBI \leq 0.7$ with exhibition of at least mild claudication (Rutherford Category > 0), or (2) $ABI \leq 0.9$ or $ABI > 1.4$ and secondary verification of $TBI \leq 0.7$ without exhibition of symptoms. In either case, if the patient displays normal ABI but PAD is suspected, then a postexercise ABI will be performed using a 1-minute treadmill test or heel-raises. A postexercise drop of $ABI \geq 20\%$ or pressure drop $\geq 30\text{mmHg}$ will be considered a positive diagnosis [16].
- A positive diagnosis of CLI will be defined by exhibition of chronic rest pain and active wounds, verified by $TBI < 0.3$.
- Patients that are enrolled in the PAD positive cohort but are not positively diagnosed for PAD using the above definition (either because their disease is improving or they were screened incorrectly) will be considered PAD negative but will not be grouped into the healthy cohort.

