8.3 Inclusion Criteria

Candidates for this study must meet ALL of the following inclusion criteria:

PAD Positive Cohort

- Subject meets PAD positive criteria set forth in Section 8.3
- Subject is willing and able to provide an informed consent.
- Subject is willing and able to comply with the study procedures.
- Subject is able to understand the study procedures.
- Subject is scheduled for vascular examination that includes noninvasive assessments as standard of care: ABI, TBI, and either a Duplex ultrasound or Angiogram.

Healthy Cohort

- Subject is willing and able to provide an informed consent.
- Subject is willing and able to comply with the study procedures.
- Subject is able to understand the study procedures.
- Subject has no history of positive PAD diagnosis and is not currently suspected of having PAD.

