7.4 Handling of Missing, Unused, and Spurious Data and Dropouts

Data that is missing or incomplete will not be imputed. Complete case data will be used where all data for the respective analysis is available for a patient or visit.

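### Section 9.7.4 ties the duplex requirement to limbs already positive on ABI/TBI, and no limb set is named for the stenosis analyses, so those analyses risk selective or differential verification

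*Protocol*

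**What the plan says.** **Imaging scope.** Protocol 9.7.4: "Duplex shall be acquired from all limbs enrolled in the study with PAD/CLI as defined via the definitions in Section 8.4". Section 8.4 lists exclusion criteria; PAD and CLI are defined in 4.1.1.1.1 from ABI, TBI, symptoms and, where needed, a postexercise ABI. Protocol 9.7 sets the scope differently: "Noninvasive testing and Duplex imaging results will be evaluated on the same leg(s) used to collect FlowMet-R data". It carries no ABI or TBI condition.

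**Entry to the PAD cohort.** Protocol 8.3: "Subject is scheduled for vascular examination that includes noninvasive assessments as standard of care: ABI, TBI, and either a Duplex ultrasound or Angiogram". This is a condition on the subject. It does not say that each measured limb is covered.

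**PAD-cohort subjects who prove negative.** Protocol 4.1.1.1.1 keeps them in the study as PAD negative, outside the healthy cohort.

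**Healthy cohort.** Protocol Section 5 and SAP Section 5 rule out imaging beyond standard of care. Healthy subjects with normal ABI and TBI are assumed to have no significant stenosis.

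**Analysis.** The stenosis ROC and the stenosis correlation are secondary endpoints (4.1.2.1 in both documents). Neither document names the limbs that enter them. SAP 7.1.3 excludes a participant from any analysis for which data are missing, and SAP 7.4 adds: "Complete case data will be used where all data for the respective analysis is available for a patient or visit". There is no imputation. SAP 7.10.2 item 2, the stenosis ROC, gives its endpoint as intervention or amputation within 7 months.

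**The concern.** The limbs that must be imaged are chosen by ABI/TBI, and FlowMet-R is then judged against that imaging. A literal reading of 9.7.4 leaves two kinds of PAD-cohort limb without a required stenosis result: a contralateral limb that was measured but is ABI/TBI-negative, and a suspected limb that proves negative. If no result is recorded, the complete-case rule removes the limb, and the SAP asks for no count of such losses.

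These limbs matter. Protocol 3.1 cites an ABI sensitivity for stenosis above 50% of roughly 15% to 79%, so stenosed limbs with a normal ABI are to be expected, and they are where a new device could add information. Protocol 5.2.2 reports that a FlowMet-R metric correlated with ABI and TBI, so selection on ABI/TBI may not be neutral for the device's AUC.

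Healthy limbs raise a second problem. If they enter as assumed negatives, their reference result comes from ABI/TBI while that of other limbs comes from imaging (differential verification). If they are dropped as missing, the analysis rests on a different population. The SAP supports either reading.

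**Working it through.** The plan gives no sample size, expected AUC or prevalence for the stenosis endpoints, so there is no figure of its own to reproduce.

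**1. Why ABI status matters.** Input: ABI sensitivity 15-79% (Protocol 3.1). Share of limbs with stenosis above 50% that fail a resting-ABI rule = 1 − sensitivity: 1 − 0.79 = 21% to 1 − 0.15 = 85%. This describes ABI alone. The postexercise route and scheduled imaging lower the share left unimaged; the added TBI condition could raise it.

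**2. Can those percentages be turned into limb counts for this study? No.** Assume 300 PAD-cohort limbs, 60% stenosed (180 and 120; neither figure is in the documents). Imaged limbs would be 180 × sensitivity + 120 × (1 − specificity), with specificity 83-99% from Protocol 3.1:
- at 0.15/0.99: 27 + 1.2 ≈ 28
- at 0.79/0.83: 142.2 + 20.4 ≈ 163

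Enrolment runs until 240 limbs with PAD are measured (Protocol 8.1, SAP 5.3), and 9.7.4 requires duplex for each. Both results contradict that floor of 240. The cohort is already selected on the PAD definition, so general ABI accuracy figures do not apply to it.

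**3. What the floor implies.** Under the same assumed 300 limbs, at most 300 − 240 = 60 fall outside the requirement. If all 60 are non-stenosed, 120 − 60 = 60 non-stenosed limbs are still imaged. Hanley-McNeil variance at AUC A, with n1 stenosed and n2 not:

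[A(1−A) + (n1−1)(Q1−A²) + (n2−1)(Q2−A²)] / (n1·n2), Q1 = A/(2−A), Q2 = 2A²/(1+A).

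At A = 0.80:
- 180 vs 120: SE 0.025
- 180 vs 60: SE 0.029

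The loss of precision is small here, but it depends on the assumed 300 and the assumed split.

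**4. How many limbs could be affected?** If every PAD-cohort subject has at least one positive limb and enrolment stops at 240 PAD limbs, the number of measured negative limbs lies between 0 (every measured leg positive) and 240 (each positive limb from a different subject whose other leg is measured and negative). Subjects who fail the definition add to this. The documents do not narrow the range.

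**5. Direction of bias.** Binormal simulation, true AUC 0.80, only ABI-positive limbs imaged. The within-class correlation between FlowMet-R and ABI is assumed, because the documents give none.

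| ABI sens/spec | r = 0 | r = 0.3 | r = 0.6 |
|---|---|---|---|
| 0.15/0.99 | 0.80 | 0.73 | 0.67 |
| 0.50/0.90 | 0.80 | 0.75 | 0.69 |
| 0.79/0.83 | 0.80 | 0.73 | 0.66 |
| 0.79/0.99 | 0.80 | 0.64 | 0.44 |
| 0.15/0.83 | 0.80 | 0.81 | 0.85 |

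The last row is an extreme corner of the cited ranges, where ABI carries almost no information on stenosis. If unimaged limbs are instead scored as negative, a true 0.80 gives 0.63 to 0.90 over the scenarios run (the first four rows, prevalence 40% or 60%, r = 0, 0.3 or 0.6). The sign of the bias therefore depends on quantities the plan does not give and on a rule it does not state.

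**The case against.** The strongest reply is that 9.7.4 sets a minimum. It does not say that only PAD/CLI limbs are imaged, every PAD-cohort subject must be scheduled for duplex or angiogram, and 9.7 already covers the legs measured with FlowMet-R. A floor and a general rule can both hold. Bilateral measurement is not universal (Protocol 9.6). The PAD definition also reaches some limbs without a low resting ABI, through ABI above 1.4 with TBI verification and through exercise testing: "if the patient displays normal ABI but PAD is suspected, then a postexercise ABI will be performed using a 1-minute treadmill test or heel-raises". The event schedules are figures that are not shown and may say more. The endpoints are secondary and, by SAP 7.2, descriptive.

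Most of this stands. It makes the loss of ABI-negative limbs a risk and not a certainty. It does not remove the risk: the inclusion criterion works per subject while the analysis works per limb, and a site reading 9.7.4 alone has no instruction to record imaging for a negative limb.

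A reader might also infer that the non-stenosed class is nearly emptied, that precision collapses, or that the AUC is pulled towards 0.5. The documents do not support these. The first two rest on ABI accuracy figures that conflict with the enrolment target of 240. The third needs a within-class correlation that is nowhere reported; Protocol 5.2.2 gives no size for the correlation and does not say that the metric was acceleration time. Nor do the documents show the opposite: if nearly all 240 PAD limbs are stenosed, non-stenosed limbs will be few whatever 9.7.4 says.

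**Conclusion.** The point holds as a risk of selective verification (PAD-cohort limbs) and differential verification (healthy limbs) in the stenosis ROC and correlation. It rests on four features of the text: the different scopes of 9.7 and 9.7.4, an inclusion criterion that works per subject, the complete-case rule, and the absence of a named limb set. The cited ABI sensitivity shows why it matters. The number of limbs affected and the size and direction of bias cannot be derived; the figures above are illustrations under stated assumptions. The wrong pointer to Section 8.4 and the wrong endpoint in SAP 7.10.2 item 2 are plain errors that need correcting in the same edit. The primary endpoints do not use imaging as their reference and are not affected. The change should be made because it is cheap.

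**What to change.** 1. **Protocol 9.7.4:** align it with 9.7. Record the stenosis result of the scheduled standard-of-care duplex or angiogram for every PAD-cohort limb with a FlowMet-R recording, whatever its ABI/TBI classification. Point the cross-reference to 4.1.1.1.1.
2. **SAP 7.10.2 items 2 and 3 (stenosis):** set the main population to imaged limbs and report how many limbs were imaged by PAD label. Add a separate sensitivity analysis in which healthy limbs with normal ABI and TBI enter as assumed negatives. This settles the tension between the assumption in SAP Section 5 and the exclusion rule in 7.1.3.
3. **SAP 7.10.2 item 2:** make stenosis the ROC endpoint in place of intervention or amputation within 7 months.
4. **Reporting:** if few PAD-negative limbs are imaged, word the conclusion as detection of stenosis among ABI/TBI-positive limbs.

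Cost: wording in both documents, some extra CRF abstraction and one additional analysis. No imaging beyond standard of care is added, so limbs outside scheduled imaging stay missing; the counts in step 2 will show how many.
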